3.2 Number of Sites and Subjects

This is a global, multicenter study in approximately 40 sites and up to 162 subjects.

3.3 Subject Enrollment

Enrollment into each cohort will occur in 2 stages:

- Cohorts A1, A3, and B1: Stage 1 will enroll and treat 14 subjects per cohort. Opening of Stage 2 for each cohort will be contingent on the number of confirmed objective responses (Part A) or pathologic responses (Part B) in Stage 1 (see [Section 10.1](#)). Additional subjects will be added in Stage 2, for a total of approximately 40 subjects (range: 38 to 48) per cohort.
- Cohort A2: Stage 1 will enroll and treat 40 subjects. Opening of Stage 2 of Cohort A2 will require a subsequent amendment following a discussion with regulatory agencies to agree on success criteria to establish an appropriate sample size.

Subjects will be enrolled using an interactive voice/web response system (IXRS). The investigative site will log into the IXRS to enroll a consented subject. Once assigned, numbers for any screening failures, nontreated, nonevaluable, or discontinued subjects will not be re-used.

3.4 Randomization and Blinding

This is an open-label study. No blinding is needed. Subjects will be enrolled into cohorts based on cancer type; no randomization will be conducted.

3.5 Data Safety Monitoring Board

The Data and Safety Monitoring Board (DSMB) will monitor the safety of the study. The DSMB will consist of individuals in relevant fields of expertise. It will convene on a regular basis (at least 2 times per year) and will review all safety information to determine whether the study should continue unchanged or whether protocol modifications are required to ensure subject safety. Details on the DSMB are provided in [Appendix B](#) and in a separate DSMB charter. The DSMB will make recommendations to the Sponsor, who will make ultimate decisions regarding study alteration or discontinuation.

3.6 Safety Review Committee

Not applicable.

3.7 Estimated Treatment Duration and Study Periods

In Part A, a subject's treatment may continue until confirmed disease progression (assessed by irRECIST), clinical deterioration as defined by the Investigator, withdrawal of consent, other study treatment withdrawal criteria are met, or until the study is terminated, whichever occurs first. In Part B, a subject's treatment duration will continue until progression as defined by RECIST prior to surgery, disease relapse after surgery, clinical deterioration as defined by the Investigator, withdrawal of consent, other study treatment withdrawal criteria are met, the subject has received CX-072 for 1 year postsurgery, or until the study is terminated, whichever occurs first. In Part B, a subject's treatment duration will be up to approximately 15 months (including 1 year postsurgery).

This Module is comprised of 3 periods:

- The Screening Period begins within 30 days prior to the first dose of study treatment (ie, Cycle 1 Day 1 Visit). Subjects for whom consent is provided will undergo Screening Period assessments to determine eligibility for the study; assessments must be performed within 30 days prior to the first dose of study treatment unless otherwise stated in this Module. Subject evaluations and tests performed specifically to determine eligibility (ie, not performed as routine standard of care) may be performed only after the informed consent form (ICF) has been signed. Assessment(s) done per standard of care prior to signing the ICF may be used for eligibility determination if completed within 30 days prior to the first dose of study treatment. The study assessments to be followed are outlined in the Schedule of Assessments in [Table 1](#) (Part A) and [Table 2](#) (Part B).
- The Treatment Period begins with the first dose of study treatment (ie, Cycle 1 Day 1) and continues up to 30 days after the last dose of study treatment (ie, End of Treatment [EOT] Visit). All scheduling is relative to first dose of study treatment (ie, Cycle 1 Day 1).
- The Follow-up Period begins after the EOT Visit. The first Follow-up Visit will be 90 (± 14) days after the last dose of study treatment and will continue every 90 (± 14) days to collect survival information and subsequent cancer treatment information. After the first 2 Follow-up Visits, this information may be collected via telephone or e-mail with the subject, designated caregiver, or referring physician offices. Survival status or date of death may be collected from public documents if the subject's status is unknown and attempts to reach the subject are unanswered.

The end of the study (EOS) for an individual subject is defined as death, loss to follow-up, withdrawal of consent, or termination of the study.

Subjects who continue in the Follow-up Period after study completion may rollover to a companion protocol after their last Follow-up Visit, if one is available, for continued observation and follow-up.

3.8 Definition of Study Completion

The study will be completed when the Sponsor has determined that sufficient data have been collected to evaluate the primary and secondary study endpoints. This is anticipated to occur approximately 3 years from when the last subject is enrolled, or when the last subject has completed the EOT Visit.

4 SELECTION AND WITHDRAWAL OF SUBJECTS

4.1 Inclusion Criteria for All Subjects (Parts A and B)

Subjects must meet all of the following criteria at Screening to be eligible for admission into the study. See additional cohort-specific inclusion criteria in [Sections 4.2, 4.3, 4.4, and 4.5](#).

1. At least 18 years of age
2. Measurable disease as defined by RECIST v1.1
3. Eastern Cooperative Oncology Group (ECOG) performance status of ≤ 1
4. Agree to provide tumor tissue and blood samples for biomarker assessment
 - Part A: Must agree to provide mandatory archival tumor tissue (formalin-fixed paraffin embedded tumor block or unstained slides) or undergo a new tumor biopsy
 - Part B: Must agree to provide tumor tissue from the initial diagnostic biopsy and prospectively agree to provide tumor tissue obtained from surgery on study for pathologic analysis and for biomarker assessment
5. Subjects with treated brain metastases are eligible if the brain metastases are stable (no magnetic resonance imaging [MRI] evidence of progression for at least 8 weeks after treatment is complete and within 28 days prior to first dose of study treatment) and the subject does not require radiation therapy or steroids. Active screening for brain metastases (eg, brain computed tomography [CT] or MRI) is not required
6. Screening laboratory values must meet all of the following criteria:
 - White blood cells $>2000/\mu\text{L}$ or $2.0 \times 10^9/\text{L}$
 - Neutrophils $\geq 1500/\mu\text{L}$ or $1.5 \times 10^9/\text{L}$
 - Platelets $\geq 100 \times 10^3/\mu\text{L}$ or $100 \times 10^9/\text{L}$
 - Hemoglobin $\geq 9.0 \text{ g/dL}$ (may have been transfused) or 90.0 g/L
 - Creatinine $\leq 2 \text{ mg/dL}$ or $176.8 \mu\text{mol/L}$ OR measured or calculated creatinine clearance (glomerular filtration rate can also be used in place of creatinine or creatinine clearance) $>50 \text{ mL/min}$
 - AST and ALT $\leq 2.5 \times$ upper limit of normal (ULN)
 - Total bilirubin within ULN (unless diagnosed with Gilbert's syndrome, those subjects must have a total bilirubin $<3.0 \text{ mg/dL}$ or $51.3 \mu\text{mol/L}$)
 - Amylase and lipase $\leq 1.5 \times$ ULN
 - International normalized ratio (INR) and activated partial thromboplastin time (aPTT) $\leq 1.5 \times$ ULN (unless subject is on therapeutic anticoagulation, at which time the INR and aPTT must be in the target therapeutic anticoagulation range)
 - Serum albumin $\geq 2.5 \text{ g/dL}$

7. Females of childbearing potential and nonsterile males must agree to practice highly effective methods of birth control (as described in [Appendix C](#)) for the duration of the study and for 6 months after the last dose of study treatment
8. The ability to understand and the willingness to sign a written ICF and adhere to study schedule and prohibitions

4.2 Additional Inclusion Criteria for Cohort A1

9. Histologically or cytologically confirmed Stage III (unresectable) or Stage IV melanoma
10. Must have BRAF V600 mutation status or consent to BRAF V600 mutation testing in accordance with local institutional standards during Screening Period
11. No prior systemic therapy for metastatic or unresectable disease and deemed to be intolerant to or refused standard first-line therapy for melanoma
 - Prior adjuvant or neoadjuvant melanoma therapy is permitted if it was completed at least 6 weeks prior to Screening, and all related AEs have either returned to baseline or stabilized. Prior adjuvant or neoadjuvant therapy with an anti-PD-1, anti-PD-L1, anti-PD-L2, or anti-CTLA-4 antibody, or any other antibody or drug specifically targeting T cell costimulation or immune checkpoint pathways is not allowed.

4.3 Additional Inclusion Criteria for Cohort A2

12. Histologically or cytologically confirmed Stage III (unresectable) or Stage IV melanoma
13. Have experienced disease progression during treatment with an anti-PD-1/PD-L1 antibody (including bispecific antibodies) given as monotherapy or in a combination not containing anti-CTLA-4 antibody as the treatment regimen immediately prior to accrual to this study, or have experienced disease progression within 6 months of adjuvant or neoadjuvant anti-PD-1/PD-L1 antibody therapy
 - Progression is defined as radiographic progression, new lesion(s) (detected radiographically or by physical exam), or clinical progression per Investigator assessment
 - Subjects with radiographic progression prior to receiving at least 12 weeks of an anti-PD-1/PD-L1 therapy must have a confirmatory scan showing progression no sooner than 4 weeks after the initial radiographic progression

4.4 Additional Inclusion Criteria for Cohort A3

14. Histologically or cytologically confirmed advanced/unresectable or metastatic urothelial carcinoma of the renal pelvis, ureter, bladder, or urethra
15. Experienced disease progression during or after receipt of platinum-containing chemotherapy for metastatic disease or recurrence within 1 year of completing prior platinum-based neoadjuvant or adjuvant therapy. Only 1 prior line of platinum chemotherapy allowed. Subjects who received at least 1 cycle of a platinum-containing regimen but discontinued due to toxicity and who were deemed unsafe to continue with platinum therapy are also eligible.

4.5 Additional Inclusion Criteria for Cohort B1

16. Histologically or cytologically confirmed resectable Stage III melanoma with 1 or more macroscopic lymph node metastases (measurable according to RECIST v1.1) that can be biopsied and no history of in-transit metastases within the last 6 months
17. Lactate dehydrogenase (LDH) within normal range

4.6 Exclusion Criteria for All Subjects (Parts A and B)

Subjects who fulfill any of the following criteria at Screening will not be eligible for admission into the study. See additional cohort-specific exclusion criteria in [Sections 4.7](#) and [4.8](#).

1. Treatment with cytotoxic chemotherapy, biologic agents, radiation, immunotherapy, or any investigational agent within 28 days prior to the first dose of study treatment. This interval can be reduced to 2 weeks for subjects who received bone-only radiation therapy or for subjects whose most recent prior therapy was a single-agent, small-molecule kinase inhibitor having a half-life of 3 days or less.
 - For Cohort A2: Prior anti-PD-1/PD-L1 antibody given as a single agent is not excluded within the 28 days prior to the first dose of study treatment. Time from last dose of prior anti-PD-1/PD-L1 inhibitor to first dose of study treatment must be at least the same length as the time interval of the prior PD-1/PD-L1 dosing schedule (eg, if prior PD-1/PD-L1 dosing was once every 14 days, then the last dose must have been at least 14 days prior to first dose of study treatment).
2. Prior therapy with a chimeric antigen receptor T cell-containing regimen
3. History of active autoimmune disease(s) including but not limited to inflammatory bowel diseases, rheumatoid arthritis, autoimmune thyroiditis, autoimmune hepatitis, systemic sclerosis, systemic lupus erythematosus, autoimmune vasculitis, autoimmune neuropathies, type 1 insulin-dependent diabetes mellitus
4. History of myocarditis regardless of the cause

5. History of intolerance to prior checkpoint inhibitor therapy defined as the need to discontinue treatment due to an irAE
6. History of toxic epidermal necrolysis or Stevens-Johnson syndrome
7. History of any syndrome or medical condition that required treatment with systemic steroids (≥ 10 mg daily prednisone equivalents) or immunosuppressive medications. However, subjects who required brief courses of steroids (eg, as prophylaxis for IV contrast or for treatment of an allergic reaction) may be eligible with Sponsor approval. Inhaled or topical steroids are permitted.
8. Baseline corrected QT interval (QTc) >470 ms. If a subject starts on a QTc prolonging drug(s), a series of electrocardiograms (ECGs) should be obtained to redefine the baseline QTc.
9. Unresolved acute toxicity Common Terminology Criteria for Adverse Events (CTCAE) v5.0 \geq Grade 1 (or baseline, whichever is greater) from prior anticancer therapy. Alopecia and other nonacute toxicities are acceptable. Hormone deficiency due to prior anticancer therapy, that is deemed stable with supplementation or does not require supplementation is allowed.
10. History of severe allergic or anaphylactic reactions to human mAb therapy or known hypersensitivity to any Probody therapeutic
11. Subjects with known human immunodeficiency virus, acquired immune deficiency syndrome, or any related illness
12. Subjects with acute or chronic hepatitis B or C
13. History of allogeneic tissue/solid organ transplant, stem cell transplant, or bone marrow transplant
14. Major surgery (eg, that required general anesthesia) within 4 weeks prior to the first dose of study treatment (and must be confirmed to be completely healed), or minor surgery (eg, not involving chest, abdomen, or intracranial structures) or gamma knife treatment (with adequate healing) within 14 days prior to first dose of study treatment (excluding biopsies conducted with local/topical anesthesia) if complete healing is confirmed
15. History of active malignancy not related to the cancer being treated within the previous 2 years, with the exception of localized cancers that are considered cured and, in the opinion of the Investigator, present a low risk for recurrence. These exceptions include, but are not limited to, basal or squamous cell skin cancer, superficial bladder cancer, and carcinoma in situ of the prostate, cervix, or breast.
16. Received a live vaccine within 30 days prior to the first dose of study treatment. Examples of live vaccines include, but are not limited to, the following: measles, mumps, rubella, chicken pox/zoster, yellow fever, rabies, Bacillus Calmette-Guérin, and typhoid vaccine.

17. Intercurrent illness including, but not limited to:

- Ongoing severe aortic stenosis
- Myocardial infarction or stroke within 24 weeks prior to first dose of study treatment
- Any of the following within 12 weeks prior to first dose of study treatment: symptomatic congestive heart failure (ie, New York Heart Association Class III or IV), unstable angina pectoris, or clinically significant and uncontrolled cardiac arrhythmia
- Nonhealing wound or ulcer within 4 weeks prior to Cycle 1 Day 1
- Active infection requiring systemic antiviral, antibiotic, or antifungal therapy within 5 days prior to first dose of study treatment

18. Pleural or pericardial effusion or ascites requiring drainage ≥ 1 time(s) per month

19. History of multiple myeloma

20. Women who are pregnant or breastfeeding

21. Any condition, in the Investigator's opinion, that would limit the subject's compliance with study requirements

22. Participating in an ongoing interventional clinical study (eg, medication, radiation, procedures) unless the subject is only being followed for long-term outcomes

4.7 Additional Exclusion Criteria for Cohort A1

23. Prior systemic treatment for advanced unresectable or metastatic melanoma and/or deemed suitable for standard first-line therapy

24. Prior adjuvant or neoadjuvant therapy with an anti-PD-1, anti-PD-L1, anti-PD-L2, or anti-CTLA-4 antibody, or any other antibody or drug specifically targeting T cell costimulation or immune checkpoint pathways

25. Prior adjuvant therapy with a BRAF or mitogen-activated protein kinase (MEK) inhibitor

26. Diagnosis of uveal, ocular, or mucosal melanoma

4.8 Additional Exclusion Criteria for Cohort A2

27. Prior treatment with an anti-CTLA-4 agent

28. Prior treatment with cell-based immunotherapy

29. More than 1 prior line of systemic anticancer therapy for unresectable or metastatic melanoma. Prior treatment with an anti-PD-1/PD-L1 antibody in both neoadjuvant/adjuvant and unresectable/metastatic settings is allowed.

30. Prior treatment with a BRAF or MEK inhibitor

31. Diagnosis of uveal, ocular, or mucocutaneous melanoma

4.9 Additional Exclusion Criteria for Cohort A3

32. Prior treatment with a PD-1/PD-L1 inhibitor or CTLA-4 inhibitor
33. More than 1 prior line of chemotherapy

4.10 Additional Exclusion Criteria for Cohort B1

34. Prior systemic treatment for melanoma
35. Diagnosis of uveal, ocular, or mucocutaneous melanoma

4.11 Study Treatment Discontinuation Criteria

Subjects MUST discontinue study treatment for any of the following reasons:

- The subject experiences confirmed disease progression as assessed by irRECIST (Part A) or disease progression prior to surgery or disease relapse after surgery (Part B)
- The subject is unwilling or unable to adhere to the protocol
- The subject withdraws consent or is lost to follow-up
- The subject experiences an adverse event (AE) that precludes further safe administration of study treatment (see also [Section 5.3.1](#))
- The subject becomes pregnant at any time during the study, including prior to the first dose of study treatment
- In the Investigator's judgment, the subject should discontinue study treatment
- The Sponsor terminates the study
- The subject experiences an intercurrent illness that prevents further administration of study treatment
- The subject requires new/other anticancer treatment

5 TREATMENT OF SUBJECTS

5.1 Study Drugs

Study treatment consists of 2 study drugs, CX-072 and ipilimumab. CX-072 is a recombinant, protease-activatable immunoglobulin G subclass 4 (IgG4) mAb prodrug (██████████) that is derived from a human mAb against the ligand PD-L1 and is intended for use in oncology indications.

Ipilimumab is a human CTLA-4 blocking antibody approved for a variety of indications (see the local prescribing information for ipilimumab).

5.1.1 Formulation and Packaging

The vial and carton labels for each study drug will include standard product information in accordance with applicable regulatory requirements.

5.1.2 Storage and Accountability

It is the responsibility of the Investigator to ensure that the clinical supplies described below are stored as specified and in accordance with applicable regulatory requirements. Drug accountability details are provided in the Core ([Appendix A](#)).

[REDACTED]

Ipilimumab

Store vials upright under refrigeration at 2°C to 8°C (36°F to 46°F). Do not freeze or shake. Protect ipilimumab from light by storing in the original carton until time of use.

5.1.3 Study Drug Preparation and Dispensing

[REDACTED]

[REDACTED]

[REDACTED]

[REDACTED]

[REDACTED]

[REDACTED]

5.2 Study Drug Administration and Dosing Regimen

5.2.1 Study Drug Administration

5.2.2 Study Treatment Dosing Regimen

CX-072 and ipilimumab are to be administered in this study as follows:

- Part A:
 - Combination treatment: 800 mg CX-072 + 3 mg/kg ipilimumab, q3w
 - Monotherapy treatment: 800 mg CX-072, q2w
- Part B:
 - Combination treatment: 800 mg CX-072 + 1 mg/kg ipilimumab, q3w
 - Monotherapy treatment: 800 mg CX-072, q2w

In Part A, subjects will be treated with 4 doses of 800 mg CX-072 IV plus 3 mg/kg ipilimumab IV combination therapy (ie, q3w on Cycle 1 Day 1, Cycle 1 Day 22, Cycle 2 Day 1 [Study Day 43], and Cycle 2 Day 22 [Study Day 64]; all ± 2 days). Three weeks following receipt of the fourth dose of combination treatment (ie, Study Day 85 [± 2 days]), subjects will receive 800 mg CX-072 IV monotherapy q2w until the occurrence of progressive disease by irRECIST, unacceptable toxicity, or the subject meets any other criterion for treatment discontinuation (Section 4.11).

In Part B, subjects will be treated with 2 doses of 800 mg CX-072 IV plus 1 mg/kg ipilimumab IV combination (ie, q3w on Cycle 1 Day 1, Cycle 1 Day 22; all ± 2 days) followed by surgical resection of the tumor on Day 43 (-2/+7 days). An additional 2 doses of 800 mg CX-072 IV plus 1 mg/kg ipilimumab IV combination will be administered approximately 6 weeks postsurgery (ie, q3w on Cycle 2 Day 1 [Study Day 85 (± 2 days)] and Cycle 2 Day 22 [Study Day 106 (± 2 days)]). Three weeks following receipt of the fourth dose of combination treatment (ie, Study Day 127 [± 2 days]), subjects will have the option to continue with 800 mg CX-072 IV monotherapy q2w following discussion and agreement of risk/benefit between the Investigator and the Sponsor Medical Monitor. Subjects may receive up to 1 year of CX-072 infusions postsurgery (including 2 postsurgery combination doses and then as monotherapy) until the occurrence of disease relapse, unacceptable toxicity, or the subject meets any other criterion for treatment discontinuation ([Section 4.11](#)).

A maximum of 4 doses of ipilimumab may be administered to any subject (Parts A and B).

5.3 Treatment Delays, Dose Modification, and Missed Doses

A minimum of 14 days is required between infusions of CX-072 and a minimum of 21 days between infusions of ipilimumab. In exceptional circumstances, an infusion may be delayed for up to 7 days. Infusions that cannot be administered in that time frame will be considered a missed dose, and the subject should come in for the next regularly scheduled visit relative to Day 1.

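### The dosing windows, the Day 1 visit calendar and the delay rule contradict the required minimum intervals between infusions, and the protocol does not say which governs

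*Combined protocol and SAP*

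**What the plan says.** **Minimum intervals.** Section 5.3 is worded as a requirement: "A minimum of 14 days is required between infusions of CX-072 and a minimum of 21 days between infusions of ipilimumab".

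**Dosing days.** Section 5.2.2 schedules Part A combination treatment "q3w on Cycle 1 Day 1, Cycle 1 Day 22, Cycle 2 Day 1 [Study Day 43], and Cycle 2 Day 22 [Study Day 64];" and gives every one of these days a window of 2 days either side. Part B uses Days 1 and 22 before surgery and Days 85 and 106 after it, with the same windows. CX-072 monotherapy every two weeks starts on Day 85 (Part A) or, as an option, Day 127 (Part B).

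**Calendar.** Section 3.7 says: "All scheduling is relative to first dose of study treatment (ie, Cycle 1 Day 1").

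**Delays.** Section 5.3 adds: "In exceptional circumstances, an infusion may be delayed for up to 7 days". An infusion that cannot be given in that time "will be considered a missed dose, and the subject should come in for the next regularly scheduled visit relative to Day 1". Section 5.3.1 adds that a CX-072 delay also delays ipilimumab.

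**Part B restart.** Section 5.2.2 places "surgical resection of the tumor on Day 43 (-2/+7 days"). It says that the next two doses of the "combination will be administered approximately 6 weeks postsurgery", and equates this with Study Days 85 and 106.

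**The concern.** The nominal spacing of the ipilimumab doses equals the minimum spacing, so nothing is left for a window that also runs backwards. A site that uses the printed windows can break the minimum. A site that protects the minimum after a late dose can be pushed out of the next window. The delay rule sharpens this: a delay of up to 7 days is permitted, but the text does not say whether later visits move with it.

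Two things are at stake. The first is safety: Section 1.5 describes the Part A combination as equivalent to the maximum tolerated dose (MTD), and 2 of 5 subjects at the next dose level had a dose-limiting toxicity. The second is data quality: exposure and the count of protocol deviations would depend on which section a site chose to follow.

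**Working it through.** **Inputs.** Minimums of 21 days (ipilimumab) and 14 days (CX-072), and a delay of up to 7 days, from Section 5.3. Dosing days, windows and surgery day from Section 5.2.2. Day 1 is held fixed because it is the anchor in Section 3.7.

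**1. Nominal schedule.** 22 − 1 = 43 − 22 = 64 − 43 = 21 days; 106 − 85 = 21 days. Surgery to restart: 85 − 43 = 42 days = 6.0 weeks. The plan's own figures reproduce.

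**2. Shortest in-window gap.** Formula: (next day − 2) − (previous day + 2), with no offset on Day 1.

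- Doses 1 to 2: 20 − 1 = 19 days.
- Part A doses 2 to 3: 41 − 24 = 17 days.
- Part A doses 3 to 4: 62 − 45 = 17 days.
- Part B Day 85 to Day 106: 104 − 87 = 17 days.

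All are below 21. None is below the 14-day CX-072 minimum.

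**3. How many in-window Part A schedules comply.** Doses 2, 3 and 4 can each fall on 5 days: 5 × 5 × 5 = 125 schedules. Write e2, e3, e4 for the offsets from Days 22, 43 and 64. The 21-day minimum requires e2 ≥ 0, e3 ≥ e2 and e4 ≥ e3. The offsets must therefore be non-decreasing values from {0, 1, 2}, which gives 10 schedules; 10/125 = 8%. In none of them is dose 2, 3 or 4 early, so the minus side of those three windows cannot be used. The same holds for the Part B Day 22 dose. The Part B Day 106 dose can be early only if the Day 85 dose was at least as early.

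**4. A 7-day delay with the next visit left on the Day 1 calendar.**

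- Ipilimumab: Day 22 dose given on Day 29; 43 − 29 = 14 days, against 21. Even the last in-window day gives 45 − 29 = 16 days.
- Two-weekly CX-072: Day 85 dose given on Day 92; next visit Day 99; 99 − 92 = 7 days, against 14.

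**5. The same delay with the minimum kept.** 29 + 21 = Day 50 and 50 + 21 = Day 71, each exactly 7 days late, which is the limit that Section 5.3 reserves for exceptional circumstances. Three weeks after Day 71 is Day 92, while Section 5.2.2 equates that point with Day 85 ± 2.

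**6. Part B surgery to restart.** Surgery may fall on Days 41 to 50 and restart on Days 83 to 87. Shortest gap: 83 − 50 = 33 days. Longest: 87 − 41 = 46 days. After surgery on Day 50 the gap is 33 to 37 days (4.7 to 5.3 weeks). Six weeks after Day 50 is Day 92, outside the restart window.

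**The case against.** The best defence is that the minimum is expressly required and no readable text lets a window override it. Read together, the rules narrow the usable window, and compliant schedules exist: the 10 found above, or a delay carried forward. That stands. A reader might infer that the protocol permits 17-day dosing, but the documents do not support this. What they contain is a contradiction with no rule of precedence.

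The delay calculation is also conditional. Section 5.3 returns subjects to the Day 1 calendar only after a missed dose, where the gap lengthens (Day 1 to Day 43 is 42 days). For a delayed dose that return follows only from the general sentence in Section 3.7. This limits step 4 but leaves open how such visits are counted.

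Three further inferences should not be drawn.

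- A reader might suppose that the two-weekly CX-072 windows also break the 14-day minimum. The readable text gives no window for those doses after the first, and the schedule tables that may hold it are not shown.
- A reader might suppose that a subject dosed late stays constrained for the rest of treatment. The 21-day minimum binds only the remaining ipilimumab doses, at most 4 in all. In Part B, the interval from Day 22 to Day 85 removes the constraint.
- A reader might see the Part B restart as a plain conflict. It is nominally exactly 42 days, the text says approximately, no minimum from surgery to restart is stated, and Day 92 is Day 85 + 7, within the exceptional delay allowance.

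Finally, the MTD argument applies to Part A only, since Part B uses 1 mg/kg ipilimumab, and the documents give no exposure or toxicity figure for a shortened interval.

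**Conclusion.** The concern holds as an unreconciled contradiction between Sections 3.7, 5.2.2 and 5.3. The firm part needs only the printed days and windows, with Day 1 as a fixed anchor: in-window ipilimumab gaps can be 17 to 19 days against a required 21, and 115 of 125 in-window Part A schedules fail the minimum. The 8% that comply is a share of possible schedules. It is not a forecast of deviations, because sites do not choose days at random and may respect the stated minimum.

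The figures of 14 days (ipilimumab) and 7 days (two-weekly CX-072) hold if a full 7-day delay is followed by a visit on the unshifted Day 1 calendar. The Part B restart is a minor point, confined to late surgery. The matter should be corrected because it concerns dosing rules at the combination's MTD in Part A and is cheap to settle.

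**What to change.** Amend Sections 3.7, 5.2.2 and 5.3 together so that the windows and the minimum intervals are compatible. The text should state:

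- which rule governs when a window and a minimum interval disagree;
- how visits are counted after a dose that is delayed but not missed;
- whether the Part B postsurgery restart follows the Study Day or the actual date of surgery.

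The schedule tables should be checked against the result. The choice of intervals and of the restart rule is a clinical one for the sponsor, and none is proposed here. The cost is amendment wording and a check in the system that schedules visits, with no extra subjects or procedures.
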